13.0 STATISTICAL METHODS

13.1 Sample Size Determination

To evaluate the primary objective for HC analysis a sample size of at least 192 evaluable sites per study product arm (IP or RS) per body site can achieve > 95% power to pass HC analysis acceptance criteria for all four objectives using one-sample t-test (two-sided), with the following assumptions.

- Two-sided test Type I error (α): 0.05
- Standard deviation and mean log reduction:

| Time Point | Study Product | Standard Deviation | | Log Reduction | |
|------------|---------------|--------------------|-------|---------------|-------|
| | | Abdomen | Groin | Abdomen | Groin |
| 30 Seconds | IP | 1.14 | 1.43 | 3.47 | 3.38 |
| 6 hours | IP | 1.22 | 1.24 | 3.43 | 3.50 |

To evaluate the primary and secondary objectives for the US FDA analysis a sample size of 280 evaluable sites per study product arm (IP, AC or NC) per body site can achieve > 95% power to demonstrate the non-inferiority of the Investigational Product (IP) as compared to the Active Control (AC) and the superiority of the IP as compared to the negative control (NC) in antimicrobial effect at 30-second (abdomen only) and 10-minute (abdomen and groin) post-product application time point for all six objectives, with the following assumptions:

- Two-sided test Type I error (α): 0.05
- Average Treatment Effect in \log_{10} CFU/cm²:

| Average Treatment Effect | Abdomen | Groin |
|--------------------------|---------|-------|
| IP – AC | 0.06 | 0.10 |
| NC – IP | 1.58 | 2.31 |

- Standard deviation for each treatment effect for Abdomen: 1.05 \log_{10}
- Standard deviation for each treatment effect for Groin: 1.2 \log_{10}

The overall power to pass both HC analysis and US FDA analysis acceptance criteria is > 90%.

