3.2 FDA Analysis

To evaluate the primary and secondary objectives for the US FDA analysis a sample size of 280 evaluable sites per study product arm (IP, AC or NC) per body site can achieve > 95% power to demonstrate the non-inferiority of the Investigational Product (IP) as compared to the Active Control (AC) and the superiority of the IP as compared to the negative control (NC) in antimicrobial effect at 30-second (abdomen only) and 10-minute (abdomen and groin) post-product application time point for all six objectives, with the following assumptions in Table 3.

Table 3: Parameters Used in Sample Size Calculations For FDA Analysis

Two-sided test Type I error (α) : 0.05		
Average Treatment Effect	Abdomen (\log_{10})	Groin (\log_{10})
IP - AC	0.06	0.10
NC - IP	1.58	2.31
Standard deviation for each product on Abdomen: 1.05 \log_{10}		
Standard deviation for each product on Groin: 1.2 \log_{10}		

The overall power to pass both HC analysis and FDA analysis acceptance criteria is > 90%.

4 Intended Statistical Software

The analyses will be performed using R version 3.6.0 (2019-04-26) [2] or higher. R libraries and versions that are used for analyses will be listed.

5 Data

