6.2.2.2 Primary Analysis

A linear regression model for each body site (abdomen or groin) will be used for primary analysis of efficacy at 10 minutes. In the model, the response is the post-product application bacterial counts at 10 minutes and predictors are the study products (IP, AC or NC) as a fixed effect and the pre-product application bacterial loads as a covariate. The average treatment effect (ATE) corrected for pre-product application bacterial loads will be estimated from the model and compared to both non-inferiority and superiority criteria (cf. Table A.3.5).

For assessment of the four primary objectives (i.e., immediate activity at 10 minutes post application on the abdomen and groin for non-inferiority and superiority):

- A non-inferiority criterion with a 0.5 \log_{10} margin will be implemented for ATE of the IP compared to the AC (i.e., if the upper two-sided 95% confidence bound of the post-product application bacterial load corrected for pre-product application bacterial load of the IP-AC is less than 0.5 \log_{10} , the non-inferiority criterion is met).
- A 1.2 \log_{10} superiority criterion will be implemented for the ATE of the IP compared to the NC (i.e., if the lower two-sided 95% confidence bound of the post-product application bacterial load corrected for pre-product application bacterial load of the NC-IP is greater than 1.2 \log_{10} , the superiority criterion is met).

A graph showing the ATE with 95% confidence intervals for post-product log CFU at 10 minutes correcting for pre-product application will be provided for each contrast (cf. Figure C.2.1 created based on the simulated data).

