6.3 Adjustments for Multiple Objectives

An overall significance level of 0.05 ($\alpha = 0.05$) is used.

This study has two sets of objectives, one for Health Canada (HC) analysis and the other for US FDA analysis. These two sets of objectives are considered independently of each other and no multiplicity adjustment between two sets of objectives is performed.

Within the HC analysis primary objectives, since the study HC efficacy analysis will declare success when and only when all four primary objectives pass HC analysis acceptance criteria, no multiplicity adjustment is required [3].

Within the FDA efficacy analysis, a gatekeeping procedure will be applied: the efficacy analysis for two secondary objectives [30-second (abdomen only) post-product application time point] will be performed only when all four primary objectives [10-minute (abdomen and groin) post-product application time point] pass the acceptance criteria. No multiplicity adjustment between primary and secondary objectives is performed. For primary objectives [10-minute (abdomen and groin) post-product application time point], since it will declare success when and only when all four primary objectives pass FDA analysis acceptance criteria, no multiplicity adjustment for the four primary objectives is required [3]. For secondary objectives [30-second (abdomen only) post-product application time point], since it will declare success when and only when all four primary and two secondary objectives pass FDA analysis acceptance criteria, no multiplicity adjustment for the two secondary objectives is required [3].

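### The FDA regression pools saline scatter into the IP-AC non-inferiority interval and treats a subject's two sites as independent, so the interval can be too narrow or too wide

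*SAP*

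**What the plan says.** For the 10-minute primary objectives, SAP 6.2.2.2 states: "A linear regression model for each body site (abdomen or groin) will be used for primary analysis of efficacy at 10 minutes". The three products enter the same model: "predictors are the study products (IP, AC or NC) as a fixed effect and the pre-product application bacterial loads as a covariate". SAP 6.2.2.3 uses the same model at 30 seconds on the abdomen.

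The non-inferiority condition, on the log10 scale, reads: "upper two-sided 95% confidence bound of the post-product application bacterial load corrected for pre-product application bacterial load of the IP-AC is less than 0.5". Superiority has its own condition on that scale: "lower two-sided 95% confidence bound of the post-product application bacterial load corrected for pre-product application bacterial load of the NC-IP is greater than 1.2". SAP 6.3 sets "An overall significance level of 0.05", so each tested bound carries 2.5%.

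Neither section names a variance structure, a robust standard error or a subject effect. SAP 6.2.2.1 tabulates SDs by product, but nothing follows from them. SAP 3.2 plans with a single value per body site: 1.05 on the abdomen and, under "Standard deviation for each product on Groin", 1.2. Protocol 3.3.1 gives every subject two different products, one on each side of the body.

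**The concern.** Ordinary least squares estimates one residual variance from all three arms and uses it for every contrast. Two features of this trial can make that standard error wrong for IP-AC.

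- **Pooling.** Saline is not part of the IP-AC comparison, yet it supplies about a third of the variance. If saline counts scatter less than IP and AC counts, the interval is too narrow. If they scatter more, it is too wide.
- **Pairing.** Some subjects carry both IP and AC. Ignoring a positive correlation between their two sites makes the interval too wide.

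Both act on the same standard error, so they have to be judged together. This interval decides three of the six FDA objectives: non-inferiority at 10 minutes on the abdomen and on the groin, and at 30 seconds on the abdomen.

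**Working it through.** **Inputs**
- n = 280 sites per arm; SD s = 1.05 (abdomen) and 1.2 (groin): SAP 3.2.
- Assumed IP-AC effects: "IP – AC | 0.06 | 0.10" (abdomen, groin), Protocol 13.1. Assumed NC-IP effects: 1.58 and 2.31.
- Subjects with both IP and AC: 27 per block × 4 blocks = m = 108 (Protocol 3.3.1; IP, AC and NC hold codes A, C and D, and each such pair has 27). m/n = 108/280 = 0.386.
- Assumptions, since the documents give neither: r = SD(saline)/SD(IP, AC), and rho = correlation between a subject's two sites.

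**The plan's own figure.** SAP 3.2 says "a sample size of 280 evaluable sites per study product arm (IP, AC or NC) per body site can achieve > 95% power" for all six FDA objectives. The standard error of a difference is s·√(2/280): 0.0887 (abdomen) and 0.1014 (groin). Power is Φ(distance to criterion / SE − 1.96):
- Non-inferiority, abdomen: 0.44/0.0887 gives 99.86%.
- Superiority, abdomen: 0.38/0.0887 gives 98.99%.
- Non-inferiority, groin: 0.40/0.1014 gives 97.64%.
- Superiority, groin: 1.11/0.1014 gives about 100%.

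The abdomen pair counts twice (10 minutes and 30 seconds): 0.9986² × 0.9899² × 0.9764 = 95.4%. The stated figure reproduces.

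**Error of the planned IP-AC interval.** The pooled variance is s²(2 + r²)/3. The correct IP-AC variance is (2s²/n)(1 − rho·m/n). The ratio of the planned to the correct standard error is therefore

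k = √((2 + r²)/3) / √(1 − 0.386·rho), and the one-sided error is 1 − Φ(1.96k).

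The denominator is 1, 0.940 and 0.898 for rho = 0, 0.3 and 0.5.

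| r | rho = 0 | rho = 0.3 | rho = 0.5 |
|---|---|---|---|
| 0.5 | k 0.866, 4.5% | 0.921, 3.6% | 0.964, 2.9% |
| 0.7 | 0.911, 3.7% | 0.969, 2.9% | 1.014, 2.3% |
| 1.0 | 1.000, 2.5% | 1.063, 1.9% | 1.113, 1.5% |
| 1.25 | 1.090, 1.6% | 1.159, 1.2% | 1.213, 0.9% |

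The two departures cancel at r = 0.81 when rho = 0.3, and at r = 0.65 when rho = 0.5. Simulations of the planned 516-subject layout agree: 4.4–4.7% at (r 0.5, rho 0), 2.8–3.1% at (0.5, 0.5), 1.2–1.7% at (1.0, 0.5) and 1.6% at (1.25, 0).

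**Half-width.** The 95% half-width from IP and AC scatter alone (rho = 0) is 1.96 × 0.0887 = 0.174 (abdomen) and 1.96 × 0.1014 = 0.199 (groin). At r = 0.5 the pooled values are 0.866 times these, 0.151 and 0.172. The differences are 0.023 and 0.027 log10.

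**NC-IP at rho = 0.** Here k = √((2 + r²)/3) / √((1 + r²)/2). At r = 0.5 this is 0.866/0.791 = 1.095, an error of 1.6% (conservative). At r = 1.25 it is 1.090/1.132 = 0.963, an error of 3.0%.

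**Candidate remedies**
- HC3 alone corrects the pooling but not the pairing. It leaves k = 1/0.940 = 1.063 (1.9%) at rho = 0.3 and 1/0.898 = 1.113 (1.5%) at rho = 0.5. Simulation gave 1.5–1.8% when sites were correlated.
- A random subject effect with a common residual variance corrects the pairing but not the pooling. Simulated error was 4.1% at (0.5, 0.5) and 3.7% at (0.7, 0.5), above the planned model's 2.8% and 2.2% in the same runs, because the offset is gone.
- Subject-clustered robust standard errors stayed between 2.1% and 3.0% in every setting run. Monte Carlo error is about 0.3 points at 4,000 runs.

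**The case against.** The strongest reply is that nothing in the documents says saline scatters less. A reader might infer that it must: IP reductions are planned with SDs of 1.14 to 1.43, the groin baseline window is only 2.0 log wide, and a saline residual SD of 1.2 looks too large beside it. The conclusion would then be that the interval is too narrow. The documents do not support that step, for five reasons.

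- SAP 3.2 plans one SD for every product, saline included.
- The 1.14 to 1.43 values are SDs of log reductions at 30 seconds and 6 hours for the HC analysis. They are not baseline-adjusted residuals at 10 minutes.
- The window limits only the baseline sample. Each later sample comes from a different sub-area (Protocol 3.3.1), and its count has no window.
- The planned means do not treat saline as a copy of baseline. On the abdomen, 3.47 − 1.58 implies a saline reduction of about 1.9 log, if baselines are similar and time points comparable.
- Counts below 1 CFU/cm² are set to 1 (SAP 6.1.1), which could compress IP and AC scatter and push r above 1.

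The reply is also right that pairing works against a too-narrow interval, that the change in half-width is small beside the planned 0.40 to 0.44 log10 distance from the margin, and that pooled-variance ANCOVA is conventional.

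What it does not remove is the dependence on r and rho. Equal SDs are a planning assumption, and two unmodelled departures that partly cancel do not give a controlled error rate.

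**Conclusion.** The point holds as a defect in the choice of standard error, without a known direction. The planned IP-AC interval has its nominal error only at r = 1 with rho = 0, or where the two departures happen to offset each other. Over r from 0.5 to 1.25 and rho from 0 to 0.5, the one-sided non-inferiority error runs from about 4.7% (simulated at r = 0.5, rho = 0) to under 2%. These ranges are assumptions. They also rest on the planned count of 108 shared subjects, which site-level baseline exclusions may change, and on the ordinary reading of a linear regression, since the SAP does not state the variance assumption in words.

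A reversed non-inferiority conclusion is likely only if the result lies close to the margin. The change is worth making because a better estimator is available at little cost and must be chosen before the data are seen.

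**What to change.** Keep the regression and its ATE estimate. State in SAP 6.2.2.2 and 6.2.2.3 that the 95% intervals use heteroscedasticity-robust standard errors clustered on subject. Apply this to all four primary and two secondary contrasts, and to each imputed data set under SAP 6.4.1. An alternative is a mixed model with a subject random effect and product-specific residual variances; it reweights the data, so the ATE estimate may shift slightly. HC3 alone, or a subject effect with a common residual variance, is not sufficient. Handle this together with any change made for the within-subject pairing, so that one estimator covers both.

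The cost is a sentence in the SAP and one option in the R code. The IP-AC interval may become wider than the pooled one. At r = 0.5 and rho = 0 it is 1/0.866, about 15% wider. In the limit r = 0 the pooled interval is 18% too narrow (k = 0.816), so the correct one is 1/0.816, about 22% wider. With equal SDs and rho = 0.5 it is about 10% narrower (0.898). The six-objective power stays at 95.4% under the planning assumptions, because that calculation already uses 1.05 and 1.2 for IP and AC.

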6.2.2.3 Secondary Analysis

A gatekeeping procedure will be applied: the efficacy analysis for two secondary objectives [30-second (abdomen only) post-product application time point] will be performed only when all four primary

objectives [10-minute (abdomen and groin) post-product application time point] pass the acceptance criteria.

A linear regression model for abdomen only will be used for secondary analysis of efficacy at 30 seconds. In the model, the response is the post-product application bacterial counts at 30 seconds and predictors are the study products (IP, AC or NC) as a fixed effect and the pre-product application bacterial loads as a covariate. The average treatment effect (ATE) corrected for pre-product application bacterial loads will be estimated from the model and compared to both non-inferiority and superiority criteria (cf. Table A.3.6).

For assessment of the two secondary objectives (i.e., immediate activity at 30 seconds post application on the abdomen for non-inferiority and superiority):

- A non-inferiority criterion with a $0.5 \log_{10}$ margin will be implemented for ATE of the IP compared to the AC (i.e., if the upper two-sided 95% confidence bound of the post-product application bacterial load corrected for pre-product application bacterial load of the IP-AC is less than $0.5 \log_{10}$, the non-inferiority criterion is met).
- A $1.2 \log_{10}$ superiority criterion will be implemented for the ATE of the IP compared to the NC (i.e., if the lower two-sided 95% confidence bound of the post-product application bacterial load corrected for pre-product application bacterial load of the NC-IP is greater than $1.2 \log_{10}$, the superiority criterion is met).

A graph showing the ATE with 95% confidence intervals for post-product log CFU at 30 seconds correcting for pre-product application will be provided for each contrast if acceptance criteria are met for all four co-primary objectives (cf. Figure C.2.1 created based on the simulated data). If acceptance criteria are not met for any of four co-primary objectives, the plot for 30 seconds will be removed from the graph as no analysis for 30 seconds is performed.

6.2.3 Safety Analysis

Skin irritation scores for each product at each post application sampling time per body location will be tabulated with frequency and percentage (cf. Table A.4.1) for ITT population set (all randomized subjects that received study product).

The statistical significance of differences in skin irritation between the study products at each post application sampling time will be evaluated by Fisher's exact test on skin irritation data summarized for safety analysis as follows: any reaction above a zero (no reaction) on the skin irritation rating scale for any category (erythema, edema, rash, and dryness) will be considered a positive signal for that substance (cf. Table A.4.3). If Fisher's exact test shows statistically significant skin irritation between the study products, follow-up analyses (e.g., Fisher's exact test for subgroup analysis) may be conducted to determine how the reactions differ (cf. Table A.4.4).

Adverse events (AEs) will be listed for all enrolled subjects (cf. Listing B.6). Whether subjects are in ITT population set (randomized subjects that received study product) will be indicated. A summary showing number and percentage of subjects with AE(s) observed will be provided for ITT population set (cf. Table A.4.2). No inferential analysis will be performed on the incidence of AEs. If any serious adverse events (SAEs) happen, more details for SAEs will be listed (cf. Listing B.7).

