3.3 Product Application Allocation and Methods to Reduce Bias

3.3.1 Randomization

The randomization scheme for the study will be provided by the Sponsor. A sufficient number of subjects will be recruited and newly randomized to meet the minimum number of evaluable product application sites per study product arm, preserving the randomization assignment. The number of evaluable product application sites per study product arm per anatomical area will be monitored to determine additional subject enrollment and randomization to meet the required evaluable sample size. Subjects who fail to meet Product Application Day baselines will not be replaced. Additional subjects will be randomized to account for product application day failures.

Subjects will be randomized to study product arms using the following block design:

Study Product Balance

Each subject will receive two different study products, one on the right side of the body and one on the left. Therefore, there are six possible study product combinations: A-B, A-C, A-D, B-C, B-D and C-D.

A minimum of 516 evaluable subjects will be required to achieve a total of a minimum of 192 evaluable product application sites for groin and abdominal regions for 60% (v/v) 1-propanol (RS) and 280 evaluable product application sites for groin and abdominal regions for the other three study product arms. Due to the imbalance of the sample size between RS and other products, RS cannot be blinded. Assuming the treatment code for RS is B and all the other three products are either A, C or D, within each small block [i.e., every 129 (516/4) evaluable subjects randomized], number of subjects who receive each product combination is shown below. With 4 blocks in total (i.e., 516 evaluable subjects), the minimum of 192 evaluable product application sites for groin and abdominal regions for 60% (v/v) 1-propanol (RS) and 280 evaluable product application sites for groin and abdominal regions for the other three study product arms can be achieved.

| Product Combination | No. of Subjects in Each Block |
|---------------------|-------------------------------|
| A-B | 16 |
| A-C | 27 |
| A-D | 27 |
| B-C | 16 |
| B-D | 16 |
| C-D | 27 |
| Total | 129 |

Left/Right Balance

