13.5.6 Safety Analysis

The statistical significance of differences in skin irritation between the study products at each post application sampling time will be evaluated by Fisher's exact test on skin irritation data summarized for safety analysis as follows: any reaction above a zero (no reaction) on the skin irritation rating scale for any category (erythema, edema, rash, and dryness) will be considered a positive signal for that substance. If Fisher's exact test shows statistically significant skin irritation between the study products, follow-up analyses will be conducted to determine how the reactions differ. No statistical analysis will be performed on the incidence of AEs.

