2.3 Study Design

This single site study is a randomized, controlled, partially blinded, design enrolling a minimum of 516 healthy volunteers, where each subject will receive two of the planned study products on the product application sites of the abdomen and/or groin. In this study, the antimicrobial activity of the investigational product (IP), a single Swabstick impregnated with 1.75 mL of 2% (w/v) chlorhexidine gluconate (CHG) in 70% (v/v) isopropyl alcohol, will be investigated according to established testing

requirements described by Health Canada (HC) and the US FDA. The study methods for this evaluation will be based on ASTM Standard Test Method E1173-15 [1].

Descriptions of study products are shown below.

- Investigational Product (IP): Single Swabstick impregnated with 2% (w/v) chlorhexidine gluconate (CHG) in 70% (v/v) isopropyl alcohol
- Reference Standard (RS): 60% (v/v) 1-propanol applied with a single Swabstick
- Active Control (AC): ChloraPrep SEPP - 2% chlorhexidine gluconate in 70% (v/v) isopropyl alcohol
- Negative Control (NC): 0.9% normal saline applied with a single Swabstick

A minimum of 516 evaluable subjects will be required to achieve a minimum of 192 evaluable product application sites for groin and abdominal regions for 60% (v/v) 1-propanol (RS) and 280 evaluable product application sites for groin and abdominal regions for each of the other three study product arms.

Due to the imbalance of the sample size between RS and other products, RS cannot be blinded and is coded as B and all the other three products will be blinded with assigned study product codes A, C, or D. More information about blinding and methods to reduce bias may be found in the protocol for this study.

The effectiveness of the neutralizer system must be validated prior to the main treatment study start date to demonstrate that the antimicrobials are effectively neutralized and there is no effect on the growth of microorganisms. GCD statistics group will not perform any summary or analysis for the neutralization validation data so this statistical analysis plan (SAP) only applies to the main treatment study.

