5.2 Data Sets Analyzed

- The full intent-to-treat (ITT) data set (all randomized subjects that received study product) will be used for the safety analysis.
- A modified intent-to-treat (mITT) data set will be used for efficacy analyses. Inclusion for the mITT data set is evaluated for each anatomical site (left and right for the groin and abdomen). For each anatomical site, product application day baseline criteria must be met (refer to Table 1 for product application day baseline criteria) in order to be included in the mITT data set.
- Analyses conducted on the mITT data set will also be conducted on the Per Protocol data set as supportive analyses when Per Protocol data are different from mITT data. The Per-Protocol data set will include evaluable product application sites from the mITT data set that adhere to defined assessments and procedures in the protocol central to patient enrollment, safety, rights or wellbeing, as well as the completeness, accuracy and reliability of study data.

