Table A.3.3: mITT/PP - Summary Statistics for FDA Analysis - Responder Rate at 6 Hours

Body Location	Product	Responder Rate
Abdomen/Groin	IP/AC/NC	n/N (%)

Note: n is number of responders and N is total number of evaluable subjects.

Table A.3.4: mITT/PP - Summary Statistics for FDA Analysis - Product Weight

Body Location	Product	Count	Mean	Median	SD	Range (Min-Max)
Abdomen/Groin	IP/AC/NC	n	x.xx	x.xx	x.xx	x.xx - x.xx

Table A.3.5: mITT/PP - Analysis Results for FDA Analysis - ATE at 10 Minutes

Body Location	Contrast	Time Point	ATE (95% CI)	Met Criteria
Abdomen/Groin	IP-AC	10 Minutes	x.xx (x.xx, x.xx)	Yes/No
Abdomen/Groin	NC-IP	10 Minutes	x.xx (x.xx, x.xx)	Yes/No

Table A.3.6: mITT/PP - Analysis Results for for FDA Analysis - ATE at 30 Seconds

Body Location	Contrast	Time Point	ATE (95% CI)	Met Criteria
Abdomen	IP-AC	30 Seconds	x.xx (x.xx, x.xx)	Yes/No
Abdomen	NC-IP	30 Seconds	x.xx (x.xx, x.xx)	Yes/No

A.4 Safety Analysis

Table A.4.1: ITT - Summary Statistics for Irritation Scores for Abdomen/Groin at Baseline/30 Seconds/10 Minutes/6 Hours

Characteristic	IP	RS	AC	NC	Overall
Erythema					
0-No reaction	n (%)	n (%)	n (%)	n (%)	n (%)
1-Mild and/or transient redness	n (%)	n (%)	n (%)	n (%)	n (%)
2-Moderate redness	n (%)	n (%)	n (%)	n (%)	n (%)
3-Severe redness	n (%)	n (%)	n (%)	n (%)	n (%)
Edema					
0-No reaction	n (%)	n (%)	n (%)	n (%)	n (%)
1-Mild and/or transient swelling	n (%)	n (%)	n (%)	n (%)	n (%)
2-Moderate swelling	n (%)	n (%)	n (%)	n (%)	n (%)
3-Severe swelling	n (%)	n (%)	n (%)	n (%)	n (%)
Rash					
0-No reaction	n (%)	n (%)	n (%)	n (%)	n (%)
1-Mild and/or transient rash	n (%)	n (%)	n (%)	n (%)	n (%)
2-Moderate rash	n (%)	n (%)	n (%)	n (%)	n (%)
3-Severe rash	n (%)	n (%)	n (%)	n (%)	n (%)
Dryness					
0-No reaction	n (%)	n (%)	n (%)	n (%)	n (%)
1-Mild and/or transient dryness	n (%)	n (%)	n (%)	n (%)	n (%)
2-Moderate dryness	n (%)	n (%)	n (%)	n (%)	n (%)
3-Severe dryness	n (%)	n (%)	n (%)	n (%)	n (%)

Table A.4.2: ITT - Adverse Events Summary

Characteristic	IP	RS	AC	NC	Overall
Adverse Events					
No	n (%)	n (%)	n (%)	n (%)	n (%)
Yes	n (%)	n (%)	n (%)	n (%)	n (%)

Note: Overall column is calculated based on overall unique subjects included in ITT.

Table A.4.3: ITT - Safety Analysis - Overall Comparisons for Erythema/Edema/Rash/Dryness

Body Location	Time Point	p-value	Conclusion
Abdomen/Groin	30 Seconds	0.xxx	Sign. Diff/No Sign. Diff
Abdomen/Groin	10 Minutes	0.xxx	Sign. Diff/No Sign. Diff
Abdomen/Groin	6 Hours	0.xxx	Sign. Diff/No Sign. Diff

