Note: If analysis is not applicable, p-value will be shown as “N/A”.

Table A.4.4: ITT - Safety Analysis - Subgroup Comparisons for Irritation Scores

Body Location	Characteristic	Time Point	Comparison	Odds Ratio (95% CI)	Conclusion
Abdomen/Groin				x.xx (x.xx, x.xx)	Sign. Diff/No Sign. Diff

A.5 Sensitivity Analysis

Table A.5.1: Pooled Analysis Results Based on Imputed Datasets for HC Objectives - Log Reduction

Body Location	Product	Time Point	Log Reduction (95% CI)	Met Criteria
Abdomen/Groin	IP	30 Seconds	x.xx (x.xx, x.xx)	Yes/No
	IP	6 Hours	x.xx (x.xx, x.xx)	Yes/No

Table A.5.2: Pooled Analysis Results Based on Imputed Datasets for FDA Objectives - ATE

Body Location	Time Point	Contrast	ATE (95% CI)	Met Criteria
Abdomen/Groin	10 Minutes	IP-AC	x.xx (x.xx, x.xx)	Yes/No
	10 Minutes	NC-IP	x.xx (x.xx, x.xx)	Yes/No
Abdomen	30 Seconds	IP-AC	x.xx (x.xx, x.xx)	Yes/No
	30 Seconds	NC-IP	x.xx (x.xx, x.xx)	Yes/No

Table A.5.3: Tipping Point Analysis for HC Objectives - Log Reduction

Body Location	Product	Time Point	Shift Parameter	Log Reduction (95% CI)	Met Criteria
Abdomen/Groin	IP	30 Seconds	-x.x	x.xx (x.xx, x.xx)	Yes
	IP	30 Seconds	-x.x	x.xx (x.xx, x.xx)	Yes
	IP	30 Seconds	-x.x	x.xx (x.xx, x.xx)	No
	IP	6 Hours	-x.x	x.xx (x.xx, x.xx)	Yes
	IP	6 Hours	-x.x	x.xx (x.xx, x.xx)	Yes
	IP	6 Hours	-x.x	x.xx (x.xx, x.xx)	No

Table A.5.4: Tipping Point Analysis for FDA Objectives - ATE

Body Location	Time Point	Contrast	Shift Parameter	ATE (95% CI)	Met Criteria
Abdomen/Groin	10 Minutes	IP-AC	x.x	x.xx (x.xx, x.xx)	Yes
	10 Minutes	IP-AC	x.x	x.xx (x.xx, x.xx)	Yes
	10 Minutes	IP-AC	x.x	x.xx (x.xx, x.xx)	No
	10 Minutes	NC-IP	x.x	x.xx (x.xx, x.xx)	Yes
	10 Minutes	NC-IP	x.x	x.xx (x.xx, x.xx)	Yes
	10 Minutes	NC-IP	x.x	x.xx (x.xx, x.xx)	No
Abdomen	30 Seconds	IP-AC	x.x	x.xx (x.xx, x.xx)	Yes
	30 Seconds	IP-AC	x.x	x.xx (x.xx, x.xx)	Yes
	30 Seconds	IP-AC	x.x	x.xx (x.xx, x.xx)	No
	30 Seconds	NC-IP	x.x	x.xx (x.xx, x.xx)	Yes
	30 Seconds	NC-IP	x.x	x.xx (x.xx, x.xx)	Yes
	30 Seconds	NC-IP	x.x	x.xx (x.xx, x.xx)	No

Table A.5.5: Sensitivity Analysis for FDA Objectives - Responder Rate at 6 Hours

Body Location	Product	Subjects Imputed to Non-responders	Responder Rate
Abdomen/Groin	IP/AC/NC	+0	n/N (%)
		+1	n/N (%)
		+2	n/N (%)
		...	n/N (%)
		+M	n/N (%)

Note: Subjects imputed to non-responders are added to the denominator (N) for the responder rate.

A.6 Demographics

Table A.6.1: ITT - Demographics

Characteristic	IP	RS	AC	NC	Overall
Age at Time of Informed Consent (Years)					

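### No between-product irritation difference with a confidence interval is planned unless the overall four-product Fisher test is significant, and the SAP makes it optional even then

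*SAP*

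**What the plan says.** Skin reactions are one of the two principal safety measures (protocol 3.1.2); the other, adverse events, gets no inferential analysis. The SAP sets the analysis population in 5.2: "The full intent-to-treat (ITT) data set (all randomized subjects that received study product) will be used for the safety analysis".

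SAP 6.2.3 and its table shells then plan three irritation outputs:

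- **Table A.4.1**, always produced: count and percentage for each score of each category (erythema, edema, rash, dryness), by product, body location and time.
- **Table A.4.3**, titled "ITT - Safety Analysis - Overall Comparisons for Erythema/Edema/Rash/Dryness": a p-value and a conclusion, *Sign. Diff* or *No Sign. Diff*. The text defines a positive as any score above zero in any category.
- **Table A.4.4**, titled "ITT - Safety Analysis - Subgroup Comparisons for Irritation Scores": odds ratios with 95% CIs. SAP 6.2.3 makes this conditional: if the "exact test shows statistically significant skin irritation between the study products, follow-up analyses" *may* be done.

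Protocol 13.5.6 has the same condition but a firmer consequence: after significance, "follow-up analyses will be conducted to determine how the reactions differ". Neither document says that the follow-up must compare the IP with each of the active control (AC), negative control (NC) and reference standard (RS).

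**The concern.** A non-significant overall test does not show that the products irritate to a similar degree. For a safety question the useful result is how large an IP excess the data still allow, which means a difference with an interval. The plan produces that only when the overall test has already rejected, and in the SAP not necessarily then.

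Efficacy is treated differently. The IP-AC and NC-IP contrasts at 10 minutes (Table A.3.5) and the exploratory IP-RS contrasts (Table A.2.6) are reported with 95% CIs whatever the result. The sample size was set for efficacy, and no power or expected rate is given for irritation. At stake is a safety report that states *No Sign. Diff* for a test with limited power and shows nothing about its precision.

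**Working it through.** **Inputs from the documents.** The protocol (3.3.1) says: "A minimum of 516 evaluable subjects will be required to achieve" the planned site counts. SAP 2.3 gives these as "192 evaluable product application sites for groin and abdominal regions for 60% (v/v) 1-propanol (RS) and 280 evaluable product application sites" for each of the other three arms. SAP 6.3 states: "An overall significance level of 0.05"; no separate level is set for the irritation tests, so 0.05 is assumed.

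**Site counts reproduced** from the block table in protocol 3.3.1, with four blocks:
- IP, AC, NC: 4 × (16 + 27 + 27) = 280 each
- RS: 4 × (16 + 16 + 16) = 192
- Subjects, two products each: (3 × 280 + 192) / 2 = 516

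The ITT set keeps sites that fail baseline, so its counts would be somewhat larger.

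**Power of the overall test.** Exact 4×2 Fisher test by full enumeration, level 0.05, n = 280/280/280/192, 6,000 simulated trials per row. Irritation rates are assumed. Sites are treated as independent, as the planned test does, although each subject receives two products.

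| IP rate | Other three | Overall test significant | *No Sign. Diff* | IP-AC Fisher test alone significant, IP higher |
|---|---|---|---|---|
| 2% | 0.5% | 0.37 | 63% | 0.21 |
| 3% | 1% | 0.40 | 60% | 0.28 |
| 4% | 1% | 0.68 | 32% | 0.54 |
| 5% | 1% | 0.87 | 13% | 0.77 |
| 5% | 2% | 0.50 | 50% | 0.41 |
| 6% | 2% | 0.72 | 28% | 0.62 |

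Three further scenarios had unequal comparator rates. In all nine, the overall test was at least as powerful as a single unadjusted IP-AC or IP-NC Fisher test. A nominally significant IP-AC or IP-NC result was hidden by a non-significant overall test in about 0.1% to 6% of trials.

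**What the missing interval would show.** Suppose IP 8/280, AC 2/280, NC 2/280, RS 1/192.
- Overall p = 0.094, so the report is *No Sign. Diff* and Table A.4.4 is not triggered.
- IP-AC: 8/280 − 2/280 = 2.86% − 0.71% = +2.1 points. With Wilson limits (l, u) for each rate, the Newcombe lower limit is d − √[(p₁ − l₁)² + (u₂ − p₂)²] and the upper limit is d + √[(u₁ − p₁)² + (p₂ − l₂)²], giving −0.2 to 4.9 points.
- The odds ratio is (8 × 278)/(2 × 272) = 4.09, Wald 95% CI 0.86 to 19.43; pairwise Fisher p = 0.106.

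No test is significant here, yet the data allow an excess of almost 5 points. The plan would not print that.

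**The less common case.** Suppose IP 12/280, AC 6/280, NC 3/280, RS 5/192. Overall p = 0.116. IP-NC is +3.2 points (Newcombe 95% CI 0.5 to 6.4), odds ratio 4.13 (1.15 to 14.81), pairwise Fisher p = 0.033. Again Table A.4.4 is not triggered.

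**The case against.** Several stronger readings are tempting, and the documents or the arithmetic do not support them.

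- **That the reader gets no estimate at all.** Table A.4.1 is unconditional, so crude differences per category can be read off and rough intervals worked out from the counts. However, it splits reactions by category. The any-category rate used by the test cannot be recovered if a site reacts in more than one category, and neither a difference nor an interval is printed.
- **That the four-product test dilutes an IP-specific excess.** The overall test was no weaker than a single pairwise Fisher test in any scenario run.
- **That the condition routinely hides significant pairwise results.** For one given comparison it seldom does (0.1% to 6%). Counting any of three comparisons, a further simulation of 3,000 trials per scenario gave 8% to 14%, but that is three unadjusted looks. The 13% to 63% in the table is mainly low power for rare events.
- **That the plan claims equal irritation.** It does not. Irritation has no acceptance criterion, and no text says *No Sign. Diff* will be read as similarity.

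It is also fair to say that an overall test before pairwise follow-up is a conventional guard against false signals, that adverse events are summarised by product without condition, and that every irritation rate used here is assumed. All of this stands. It limits the point to reporting, but does not justify withholding a descriptive interval on a principal safety measure.

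**Conclusion.** The point holds as a reporting gap. SAP 6.2.3 withholds every between-product irritation estimate with a CI unless the overall Fisher test is significant. Even then the SAP makes the follow-up optional, while protocol 13.5.6 makes it definite. When the overall test is not significant, the report gives per-category counts and percentages plus *No Sign. Diff*, with no any-category rate, difference or interval.

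With equal comparator rates of 0.5–2% and IP rates of 2–6%, a real excess would end that way in about 13% to 63% of trials. The range rests on assumed rates, independent sites and the minimum evaluable counts; the documents offer no benchmark for a relevant excess. Efficacy conclusions are unaffected. The change is worth making because it is cheap and concerns a principal safety measure.

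**What to change.** - Make Table A.4.4 unconditional. For each body location and post-application time, report the any-category positive rate per product and the IP-AC, IP-NC and IP-RS differences with 95% CIs.
- Label these descriptive and unadjusted for multiplicity. There are 2 locations × 3 times × 3 comparisons = 18 intervals, so an occasional one will exclude zero by chance. That is the one small downside.
- Keep the overall Fisher p-value as supplementary, and state that *No Sign. Diff* is not evidence of similar irritation.
- Reconcile *may* in SAP 6.2.3 with *will* in protocol 13.5.6.

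The cost is a change of wording in the SAP and one table shell. No new data are needed.
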